6.1.5 Visit Windows

As subjects do not always adhere to visits as scheduled in the study protocol, the following rules will be applied to map each subject's assessment visits to analysis visits, based on the timing of their assessment visits, relative to their Study Day 1. Visit mapping is applied to all visits (scheduled, unscheduled, hospital discharge and early termination) for laboratory assessments, vital sign assessments and exploratory endpoint assessments. Due to differences in visit schedules for the

assessments, distinct mapping methods are used for each type of assessment. A detailed list of the parameters and the mapping rules to be applied is provided in [Appendix 5](#). In cases where multiple assessments for a parameter are recorded within a single visit window, distinct rules are applied to laboratory assessments, vital signs, and exploratory endpoints, respectively because lab parameters and vital signs are measured before and after exchanges for SMT+PE 5% group.

For laboratory and vital sign assessments:

- In the treatment period, if 2 or more assessments are mapped to the same visit window where an exchange occurred. Take the assessment closest to the scheduled exchange date/time visit target day to be used in the analysis.
- If 2 or more assessments are mapped to the same visit window, then the non-missing assessment closest to the scheduled visit target day will be used in the analysis.
- If 2 assessments are equidistant from the visit target day, the later non-missing observation will be used in the analysis.
- If in the treatment period, two assessments occur on the same date and the above rules cannot be applied to identify a record to be used in the analysis, take the treatment scheduled timepoint visit in the analysis.
- For safety laboratory visits, if the screening and Treatment Day 1 visit occur on the same date and time use the ascension number to determine if this is a duplicate visit and only pick one record.

For exploratory endpoints:

- If 2 or more assessments are mapped to the same visit window, then the non-missing assessment closest to the scheduled visit target day will be used in the analysis.
- If 2 assessments are equidistant from the visit target day, the later non-missing observation will be used in the analysis.
- If in the treatment period, two assessments occur on the same date and the above rules cannot be applied to identify a record to be used in the analysis, take the treatment scheduled timepoint visit in the analysis.

Analysis visits will be used for all efficacy and safety summaries. If specified in the endpoint description the hospital discharge visit will be summarized separately. All visits will be presented in the listings, and the analysis visit will be flagged.

6.1.6 Adverse Events

AEs will be classified as treatment-emergent AEs (TEAEs) or non-TEAEs based on the comparison of AE onset date/time with the start date/time of study treatment. A TEAE is defined as an AE which occurs between the start of study treatment and the final visit of the clinical study. For the SMT + PE-A 5% treatment group, start of study treatment is defined as an AE occurring during or after the first plasma exchange. For the SMT treatment group, it is assumed that subjects were already receiving SMT per institutional standards at the time of randomization; therefore, the start of study treatment will be defined as an AE occurring at or after randomization.

A non-TEAE will be defined as an AE which occurs prior to the start of study treatment.

An AE with incomplete start date/time will be determined to be a TEAE or non-TEAE using the conservative rule specified in [Appendix 3](#).

Adverse events with missing end date will be considered ongoing.

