8.2.1 Adverse Events

Adverse events (includes suspected ADRs) occurring at any time between signing of the subject’s ICF and the last day of the subject’s participation (Day 90 visit or early discontinuation visit) in the clinical study will be reported and recorded on the appropriate subject’s eCRF entry and subject’s source documents.

It is the investigator’s responsibility to ensure that all AEs including suspected ADRs are appropriately recorded.

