8.2.3 Clinical Laboratory Evaluations

Considering the medical history and decompensated liver disease inherent in subjects with ACLF, certain laboratory abnormalities, while clinically significant, will be expected in this medical context, and would not indicate treatment-emergent worsening or a new AE (being instead an extension of medical history/underlying pre-existing conditions). Examples include: low platelet count, decreased albumin, prolonged prothrombin time/INR, elevated bilirubin, and abnormal transaminases. These conditions would be expected laboratory consequences of cirrhosis/decompensated liver diseases. These results would not be considered individual AEs as they most likely reflect manifestations of existing cirrhosis and hepatic decompensation, unless abnormalities worsen after initiation of study treatment and become accentuated to a medically significant degree in a treatment-emergent fashion.

Central clinical laboratory data for renal, hepatic, and hematological parameters will be listed for each clinical study subject.

The investigator will be required to classify laboratory results out of the normal range reported by the central laboratory as clinically significant or not according to his/her criteria.

GRIFOLS
 
Bioscience Industrial Group
	Number	BIG-CL-PRT-000002	Version	6.0	Status	Retired	Effective Date	29-Mar-2023
	IG1407 - Effects of Plasma Exchange with Human Serum Albumin 5% (PE-A 5%) on Short-term Survival in Subjects with "Acute-On-Chronic Liver Failure" (ACLF) at High Risk of Hospital Mortality						Page	67 of 102

Laboratory results out of the normal range judged by the investigator as clinically significant will be considered AEs.

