8.3.3 Adverse Event Definitions

8.3.3.1 Adverse Events

An AE is defined as any untoward medical occurrence in a subject or clinical investigation subject administered a medicinal product or study treatment and which does not necessarily have a causal relationship with this administration. An AE can therefore be any unfavorable and unintended sign (including any abnormal laboratory finding, for example), symptom, or disease temporally associated with the use of a medicinal product, whether or not considered related to the medicinal product. This includes worsening of a pre-existing condition or increase in frequency of a pre-existing condition.

An AE is also defined as any occurrence that is new in onset, expected, or aggravated in severity or frequency from the baseline condition, or abnormal results or diagnostic procedures including laboratory test abnormalities.

In this clinical study, deterioration of the targeted disease and symptoms associated with the targeted disease will not be considered an AE as long as the deterioration is anticipated and there is no evidence suggesting a causal relationship between the study drug and the AE. Anticipated disease progression includes, but not limited to HE, gastrointestinal (GI) bleeding, portal hypertension, ascites, spontaneous bacterial peritonitis, HRS, and associated organ/system failure(s) (eg, liver, kidney, brain, coagulation, circulation, and/or lung) (see [Section 8.3.10](#)).

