8.3.8 Adverse Event Documentation

All AEs and SAEs occurring after the subject has **signed the ICF through the Final Visit (ie, end of study [Day 90 visit] or Early Discontinuation Visit)** must be fully recorded in the subject’s eCRF and SAE form (if serious) as well as in the medical record. If no AE has occurred during the study period, this should also be indicated in the eCRF.

It is the responsibility of the investigator to ensure that AEs are appropriately recorded.

At each visit, AEs will be elicited by asking the individual a non-leading question such as “Do you feel different in any way since the last visit?” Moreover, AEs will also be collected

GRIFOLS	Number						BIG-CL-PRT-000002		Version		6.0		Status		Retired		Effective Date		29-Mar-2023		
	IG1407 - Effects of Plasma Exchange with Human Serum Albumin 5% (PE-A 5%) on Short-term Survival in Subjects with "Acute-On-Chronic Liver Failure" (ACLF) at High Risk of Hospital Mortality																				
																			Page		71 of 102
Bioscience Industrial Group																					

through directly observed events or spontaneously volunteered by the subject. Clearly related signs, symptoms, and abnormal diagnostic procedures should preferably be grouped together and recorded as a single diagnosis or syndrome wherever possible.

The following variables must be recorded in the AE eCRF:

- The verbatim term (a diagnosis is preferred)
- Date/time of onset
- Date/time of resolution
- Severity (mild, moderate, severe)
- Causality (unrelated/not related, possibly related, definitely related)*
- Seriousness (yes, no)
- Action taken (with regard to IP)
- Other action (to treat the event)
- Outcome and sequel (follow-up on AE)

* An AE occurring before subject’s exposure to treatment will be labeled as “unrelated/not related”.

If it is a pre-existing AE that gets worse regarding intensity or frequency, it should be indicated.

For AEs that occur during a PE-A 5% session, the time of onset of the AE and the time of AE change materially in intensity and/or resolve will be captured in the eCRF.

In addition to the investigator’s own description of the AEs, each AE will be encoded according to the Medical Dictionary for Regulatory Activities (MedDRA).

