9.1.3.1 Adverse Events

Adverse events will be coded and classified using MedDRA® terms (system organ class and preferred terms).

When a causal relationship of an AE is classified by the investigator as definitely or possibly related, the event will be defined as a suspected ADR. A suspected ADR with a causal relationship of “definitely related” will be defined as an AR. The sponsor will consider the investigator’s causality assessment and also provide its own assessment. If there is any disagreement in causality assessment between the investigator and the sponsor, a separate summary of suspected ADRs/ARs will be provided.

For summary purpose, AEs will be classified as treatment-emergent AEs (TEAEs) or non-TEAEs depending on the comparison of AE onset date/time with the start date/time of study treatment. A TEAE will be defined as an AE which occurs between the start of study treatment and the final visit of the clinical study. A non-TEAE will be defined as an AE which occurs prior to the start of study treatment. Non-TEAEs and TEAEs will be summarized separately.

In addition, TEAEs, including suspected ADRs, will be summarized by each treatment group, system organ class, preferred term, causal-relationship, severity, and seriousness (serious versus non-serious) using descriptive statistics. At each level of summarization, a

subject will only be counted once per system organ class or preferred term using the most severe AE or the AE with the strongest causal relationship to the treatment.

AEs (including suspected ADRs) temporally associated with PE-A 5% (ie, those occurring during a PE session or within 72 hours after the completion of a PE session) will be summarized by presenting incidences and percentages and listed.

Subjects with SAEs, AEs leading to death, or who withdraw from the study because of an AE will also be individually listed and summarized.

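### The TEAE definition looks only at onset, so an adverse event that began before treatment and worsened on it is left out of the TEAE summaries whenever the site keeps its original record

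*SAP*

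**What the plan says.** **The classification rule.** SAP 6.1.6 sorts AEs "based on the comparison of AE onset date/time with the start date/time of study treatment". Protocol 9.1.3.1 does so "depending on the comparison of AE onset date/time with the start date/time of study treatment" and adds: "A non-TEAE will be defined as an AE which occurs prior to the start of study treatment". In the SAP, treatment starts at the first plasma exchange for SMT+PE-A 5% and at randomization for SMT alone. SAP Appendix 3 supplements the rule for incomplete start dates and times only.

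**What counts as an AE.** Protocol 8.2.1 collects AEs from signature of the consent form, and screening can last up to 10 days. Protocol 8.3.3.1 says of its AE definition: "This includes worsening of a pre-existing condition or increase in frequency of a pre-existing condition". It adds a second definition that takes in "any occurrence that is new in onset, expected, or aggravated in severity or frequency from the baseline condition". Protocol 8.2.3 does not treat expected laboratory abnormalities of cirrhosis as AEs "unless abnormalities worsen after initiation of study treatment and become accentuated to a medically significant degree in a treatment-emergent fashion".

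**How worsening is recorded.** Protocol 8.3.8 says: "If it is a pre-existing AE that gets worse regarding intensity or frequency, it should be indicated". The variables it requires for each AE include onset and resolution, but no date of worsening. The same section assigns the unrelated category to any AE that occurs before exposure.

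**What is tabulated.** SAP 10.1 gives pre-treatment AEs a row in the overall summary, a table by system organ class and preferred term, and a place in the full listing with a treatment-emergent flag. Its other AE summaries are built on TEAEs.

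**The concern.** The protocol regards aggravation of an existing condition as an adverse event, and in its laboratory section it describes on-treatment worsening as treatment-emergent. The derivation that fills the safety tables has no step that carries this through. An AE that is mild in screening and becomes severe, serious or fatal after treatment starts can therefore be reported as a pre-treatment event, with neither its final severity nor its seriousness tabulated.

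This matters here because patients enter with organ failure, and protocol 8.3.1 lists anaemia, coagulation disorders and hypotension among the events expected with plasma exchange. These are conditions that may already be present as AEs when treatment begins. At stake is how completely the TEAE tables, and the suspected-ADR counts that protocol 8.1 names as main safety variables, describe worsening on treatment. The efficacy analysis is not affected.

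**Working it through.** The plan gives no figure on this point and no formula applies, so the check follows one event through the text.

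Take an AE with onset after consent and before treatment start. It is still ongoing at treatment start and increases in severity afterwards.

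1. **Is it collected?** Yes. Collection runs from consent (protocol 8.2.1).
2. **Is the worsening itself an AE?** Yes, under protocol 8.3.3.1.
3. **Must it have its own record or onset date?** The documents do not say. Protocol 8.3.8 requires only an indication. It does call for the time of a material change in intensity, but only for AEs that occur during a PE-A 5% session. The eCRF completion instructions are not part of the documents.
4. **How is it classified?** This depends on step 3:
   - *Worsening entered as a new AE:* onset falls after treatment start, so it is a TEAE under the rule as written.
   - *Original record kept:* onset falls before treatment start, so it is a non-TEAE. Appendix 3 does not help, because the start date is complete.
5. **Where does the kept record appear?** In the SAP 10.1 grid, the row for AEs with pre-treatment onset is marked for system organ class and preferred term only.

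| SAP 10.1 output | Worsening entered as new AE | Original record kept |
|---|---|---|
| Non-TEAE row in overall summary | no | yes |
| Pre-treatment-onset table by SOC and preferred term | no | yes |
| Full AE listing with flag | yes | yes |
| TEAEs by severity; TEAEs by causality | yes | no |
| Serious TEAEs | if serious | no |
| TEAEs leading to death or to withdrawal | if applicable | no |
| Temporally associated TEAEs (PE arm) | if within a session or 72 hours after it | no |
| Suspected ADRs | if judged related | no, because an AE before exposure is labeled unrelated |

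The SAP does handle records that straddle treatment start elsewhere. Under 6.1.7, a medication begun earlier and continuing past that point counts as concomitant. AEs have no comparable rule.

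**Size.** The number affected is the product of three quantities: subjects with an AE that began before treatment and is ongoing at its start, the share of these that worsen, and the share of worsenings not entered as a new AE. The documents give none of them. The planned 190 per arm is not a safe base either, because the SAP (section 2) reports early termination. No count or percentage is offered.

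**The case against.** **The events are not hidden.** A reader might infer that they drop out of the safety tables altogether. They do not: they remain in the non-TEAE row, the pre-treatment-onset table and the flagged listing. Protocol 9.1.3.1 also promises listings and summaries of subjects with SAEs, AEs leading to death and AE withdrawals without limiting these to TEAEs. This stands. What is missing is the TEAE breakdown, and the SAP's own serious, death and withdrawal tables are limited to TEAEs.

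**A diligent site would enter a new AE.** Worsening meets the AE definition, and an investigator who thinks it related can hardly say so on a record labeled unrelated by rule. This stands as a reason why many cases may be classified correctly. It does not close the gap, because nothing requires the new record.

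**The pilot's thrombocytopenia.** A reader might infer that the severe thrombocytopenia seen in the pilot (protocol 2.2) would be lost. The documents do not support that. Those subjects had low platelets at baseline, and protocol 8.2.3 treats a low count as expected and not an AE until it worsens after treatment start. The later fall would be a first AE with post-treatment onset, hence a TEAE.

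**Other outputs show aggravation.** Laboratory values and vital signs are summarized as change from baseline and as pre- to post-exchange difference (SAP 10.3, 10.4), and protocol 9.1.3.3 flags clinically significant vital-sign abnormalities during a session as temporally associated AEs. This stands in part. These are mostly group statistics, and the low/normal/high shift tables cannot show a low value becoming lower.

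**The affected set is narrow.** The event must start in a short window and still be ongoing. Anticipated disease progression without evidence of a causal link is not an AE at all and is tabulated separately (SAP 10.2). This also stands.

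**Conclusion.** The definition is incomplete and does not match the protocol's own treatment of worsening. It misclassifies any AE that began before treatment, worsened on it, and was left on its original record. The effect is limited to the TEAE-based summaries and the suspected-ADR counts.

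The conclusion rests on one condition that the documents leave open: that some sites indicate the worsening without opening a new record. It would fall away if the eCRF instructions required a separate AE with its own onset date and causality assessment.

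The size is unknown. A reader might also infer that more harm is removed from the plasma exchange arm. That would follow only if exchange aggravates existing AEs more often than SMT alone does and the recording practice is similar in both arms, and the documents show neither. The change is worth making because it is cheap and settles the classification before the tables are read, not because a distortion has been demonstrated.

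**What to change.** Amend SAP 6.1.6 so that a TEAE is either

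- an AE with onset at or after the start of study treatment as already defined for each arm, or
- an AE with earlier onset that increased in severity, frequency or seriousness after that start.

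Identify the second group from the worsening indication that protocol 8.3.8 requires, together with a pre-lock review of all pre-treatment AEs ongoing at treatment start. Where the timing of the worsening cannot be established, classify the event as a TEAE, which matches the conservative default in Appendix 3. Record the change against protocol 9.1.3.1 in SAP section 12. Because a reclassified record may still carry the automatic unrelated label, say so in a footnote to the causality and suspected-ADR tables.

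New site instructions would come too late to alter recording, since the SAP gives the last patient visit as April 14, 2025. The documents do not say whether the database has been locked. If it has, the derivation can use only the indication as recorded.

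The cost is one extra derivation, one review of a limited set of records, and slightly higher TEAE counts in both arms. The documents show no dated worsening field, so part of the review may have to be manual.

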8.3.1 Warnings/Precautions

For complete information on Albutein 5% refer to the IB.

Plasma Exchange is a safe technique that may induce very well-known and therefore preventable and controllable AEs, according to the guidelines provided below. Considering the special vulnerability of the subjects studied, a number of precautions (in addition to the habitual measures) will be taken to minimize the risks of the procedure:

- PE will be carried out by specialized certified personnel, under direct and continuous supervision by the specialized physicians (intensivists, hepatologists, and hematologists).
- Vital signs and laboratory test parameters will be monitored more frequently than usual.

There are AEs that may be expected during the replacement procedure, due to the process of apheresis, the replacement fluid used, or as a result of the subject disease or idiosyncrasy. These AEs include, but not limited to, hypocalcaemia (manifesting as paresthesias, headache, vision alterations, nausea, cramps and chest oppression), anaemia and coagulation disorders secondary to coagulation factor dilution (mainly hypofibrinogenemia, with possible minor bleeding associated to severe thrombocytopenia), hypotension (accompanied by paleness, perspiration, bradycardia, nausea, vomiting, syncope, sphincter relaxation and seizures) (though the risk is minimal, since the infusion amount is equivalent to the extracted amount), allergic reactions with urticaria, dyspnea, wheezing, hypotension, tachycardia, facial reddening and palpebral edema, and AEs related to vascular access. Other events may be of psychological origin or may be inherent to the process, such as anxiety, headache, nausea, immunoglobulin level decreased, anemia, or pain after remaining immobile for several hours. However, these AEs will still be required to be reported.

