9.7 Subject Populations for Analysis

There will be 3 analysis populations in this study, 2 populations for efficacy assessment and 1 population for safety evaluation.

The ITT population is defined as subjects who are randomized. The ITT population will be used for all efficacy analyses. Subjects will be grouped according to the treatment to which they are randomized in all efficacy analyses.

GRIFOLS
 
Bioscience Industrial Group
	Number	BIG-CL-PRT-000002	Version	6.0	Status	Retired	Effective Date	29-Mar-2023
	IG1407 - Effects of Plasma Exchange with Human Serum Albumin 5% (PE-A 5%) on Short-term Survival in Subjects with "Acute-On-Chronic Liver Failure" (ACLF) at High Risk of Hospital Mortality						Page	79 of 102

The PP population is defined as the subset of subjects included in the ITT population who do not present major protocol violations which might have an impact on the primary efficacy analysis and receive at least the first 2 PE-A 5% sessions (SMT+PE-A 5% treatment group) or survive more than 2 days following randomization (SMT control group). The primary efficacy analyses will be carried out using the PP population in order to confirm the results based on the ITT population.

The Safety population is defined as the subset of subjects who receive at least one PE-A 5% treatment or SMT. Safety analyses will be based on this population. Subjects will be grouped according to the treatment they actually received in all safety analyses.

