6.1.2 Day 1 Definition and Study Drug Administration

The Day1 visit is the planned date of randomization and typically, also the date of the first infusion of study treatment. In general, for baseline characteristics, disease history, medical history as well as efficacy endpoints, the Study Day 1 refers to the date of randomization (from the 'ELIGIBILITY' eCRF), while for previous and concomitant medications, exposure, and safety endpoints, the Study Day 1 refers

Instituto Grifols, S.A. / Protocol IG1407

to the date of the first exchange of study treatment or the randomization date for SMT Alone. For SMT and PE-5% if the date of randomization and the date of the first exchange of study treatment are different, the study day will not be the same for all endpoints.

All efficacy and safety assessments at all visits will be assigned a study day relative to Study Day 1.

Study day or relative day for an event/assessment visit on or after the respective Study Day 1 (\geq date of Study Day 1) is defined as:

Event date/Assessment Visit date - (Study Day 1 date) + 1

Study day or relative day for an event/assessment visit prior to the respective Study Day 1 ($<$ date of Study Day 1) is defined as:

Event date/Assessment Visit date - (Study Day 1 date)

There is no 'Day 0'.

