6.4.1 Safety Population

The Safety population is defined for the SMT + PE-A 5% treatment group as the subset of subjects who received at least one PE-A 5% treatment; and is defined for the SMT alone treatment group as all subjects randomized to SMT, assuming that all subjects in the SMT arm received the SMT treatment. Safety analyses will be based on this population. Subjects will be grouped according to the treatment they actually received in all safety analyses.

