9.3.13 Ascites Assessment

Ascites assessment will be collected for each treatment day and follow-up visit. The grade of ascites and refractory ascites will be summarized by visit and by treatment.

10 Safety Analysis

Unless otherwise noted, all Safety listings and summaries will be based on the Safety population.

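### The TEAE window and the Safety population start at randomization for SMT but at the first exchange for SMT+PE-A 5%, so pre-exchange events reach the comparative AE tables in one arm only.

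*SAP*

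**What the plan says.** SAP 6.1.6 classifies an AE by comparing its onset date and time with the start of study treatment, and sets that start by arm. In the PE arm, "start of study treatment is defined as an AE occurring during or after the first plasma exchange". In the SMT arm, "the start of study treatment will be defined as an AE occurring at or after randomization"; the reason given is that these subjects are assumed to be on institutional SMT already. Appendix 3 carries the same split into the rule for incomplete onset dates.

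SAP 6.4.1 defines the Safety population of the PE arm "as the subset of subjects who received at least one PE-A 5% treatment", whereas it "is defined for the SMT alone treatment group as all subjects randomized to SMT". Under SAP Section 10, unless otherwise noted, "all Safety listings and summaries will be based on the Safety population".

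The protocol is worded differently. Section 9.7 states: "The Safety population is defined as the subset of subjects who receive at least one PE-A 5% treatment or SMT". It groups subjects by treatment received. Protocol 9.1.3.1 ties TEAEs to the start of study treatment without separating the arms. SAP Section 12, which lists changes from the protocol, mentions neither the narrower Safety population nor the arm-specific start.

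SAP 6.1.2 says that randomization and first exchange typically share a date, and provides for the case "if the date of randomization and the date of the first exchange of study treatment are different".

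**The concern.** Both arms receive SMT from randomization; the PE arm is SMT plus exchange. The SAP's justification for starting the SMT clock at randomization is therefore equally true of the PE arm and does not explain a later clock there. Same-day treatment does not remove the difference, because onset is compared by date and time: an event an hour before session 1 is non-treatment-emergent in a PE subject, while an event just as soon after randomization in an SMT subject is a TEAE.

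At stake is the descriptive comparison of TEAEs, serious TEAEs and TEAEs leading to death. The protocol bases safety comparisons on review of descriptive statistics (9.1.3), so no model downstream would correct a difference in windows. For subjects who are exchanged, the window difference can only lower the PE arm's count. It also keeps any harm from preparing for the procedure out of the main tables. Protocol 8.3.1 names "AEs related to vascular access" among the expected events.

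**Working it through.** **Inputs**
- 90-day mortality 50% (SMT) and 35% (PE), control hazard 0.0077 per day, hazard ratio 0.6215, 190 subjects per arm: SAP 6.2 and Protocol 9.2.
- 28-day mortality 34% in ACLF-1b/2/3a at diagnosis: Protocol Table 2-2.
- Gap between randomization and first exchange: not in the documents. Assumed range 0.25 to 2 days.
- Enrolment after early termination is not stated, so the planned 190 is used.

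**Step 1. Reproduce the plan's figures.**
- Control hazard: −ln(0.50)/90 = 0.0077. PE hazard: −ln(0.65)/90 = 0.0048. Ratio: ln(0.65)/ln(0.50) = 0.6215, as stated.
- Chi-square without continuity correction: 170 per arm; 340/0.90 = 378, against 380.
- Log-rank: 139 events (Schoenfeld) to 145 (Freedman), against 141; 141/0.425 = 332; 332/0.90 = 369, against 370.

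The plan's figures hold, and nothing in this point changes alpha, power or sample size.

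**Step 2. Trace an AE with onset after randomization.**

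| Output | SMT | PE, onset before session 1, later exchanged | PE, never exchanged |
|---|---|---|---|
| Safety population (SAP 6.4.1) | yes | yes | no |
| TEAE, serious TEAE and fatal TEAE tables (SAP 10.1) | yes | no | no |
| Non-TEAE row and SOC/PT table (SAP 10.1) | no | yes, mixed with screening AEs | no |
| Flagged AE listing (SAP 10.1) | yes | yes | no |
| Suspected ADR | by investigator judgement | no: labelled unrelated (Protocol 8.3.8) | no |
| 72-hour session-associated table | not applicable | no | no |
| Primary survival analysis, deaths (SAP 6.4.2, 9.1.1) | yes | yes | yes |

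The last column follows from SAP 6.4.1 and the default in Section 10. As the SMT set is defined by randomization to SMT, a never-exchanged PE subject belongs to neither arm's Safety population. Under Protocol 9.7 that subject would be included, but grouping by treatment received could place the subject under SMT.

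**Step 3. Size the gap.** Expected all-cause deaths among 190 subjects = 190 × (1 − exp(−hazard × gap)).

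| Daily hazard | 0.25 day | 0.5 day | 1 day | 2 days |
|---|---|---|---|---|
| 0.0048 (plan, PE) | 0.23 | 0.45 | 0.91 | 1.81 |
| 0.0077 (plan, SMT) | 0.37 | 0.73 | 1.46 | 2.90 |
| 0.0148 = −ln(1 − 0.34)/28 (front-loaded) | 0.70 | 1.40 | 2.80 | 5.56 |

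The plan implies 190 × 0.35 = 66.5 to 190 × 0.50 = 95 deaths per arm over 90 days. No rate of access complications is given, so these cannot be sized.

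**The case against.** Starting TEAEs at first exposure is what Protocol 9.1.3.1 leads to for the PE arm, the SAP explains its SMT rule, and the gap is normally under a day. AEs are collected from consent (Protocol 8.2.1). All of that stands, and it limits the size of the problem. It does not justify different windows in a between-arm comparison, and elsewhere the SAP does use a common start: new infections count from randomization in both arms (SAP 9.3.9, 9.3.10).

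Three stronger readings are tempting, and the documents do not support them.

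- A reader might infer that early deaths and access complications vanish from the PE arm. For subjects later exchanged they do not: SAP 10.1 gives non-TEAEs their own row and SOC/PT table, and lists every AE with a flag. Deaths of all randomized subjects, exchanged or not, count from randomization in the primary analysis, subject to the same transplant censoring in both arms. Only never-exchanged PE subjects leave the safety output.
- A reader might take 2.8 deaths per day of gap as the size of the bias. That is the front-loaded hazard over a full day, applied to all-cause deaths. Anticipated ACLF progression is generally not an AE (Protocol 8.3.10), and deaths unequivocally due to progression are not SAEs (8.3.11.2), in either arm.
- A reader might conclude that pre-session access complications are wholly under-counted. That is true of the TEAE tables by definition, but they still reach the non-TEAE table. Protocol 8.3.1 lists access events among those expected during the procedure; neither document says that the line is placed between randomization and session 1, and Protocol 6.1.1.2 refers to a central line in all subjects.

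It is also fair to say that the effect of 6.4.1 on PE percentages has no fixed direction. Never-exchanged subjects leave numerator and denominator together, so dropping some without events would raise the PE rate.

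**Conclusion.** The concern holds in this limited form. The AE window and the Safety population are defined differently by arm, for a reason that applies to both. Events between randomization and first exchange count in the main comparative tables for SMT only, and never-exchanged PE subjects are absent from all safety output, a narrowing of Protocol 9.7 that SAP Section 12 does not declare. The window effect runs one way. The primary survival result is untouched.

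The size is probably small: about 0.2 to 2.9 all-cause deaths per 190 subjects at the plan's hazards, or up to 5.6 with the front-loaded hazard. This rests on an assumed gap of 0.25 to 2 days, constant hazards and planned enrolment. Given those assumptions it is an upper bound on fatal AEs, because many such deaths would be recorded as progression. For non-fatal events and access complications the documents give no basis for a number.

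**What to change.** In SAP 6.1.6 and Appendix 3, use randomization as the AE window start in both arms for the between-arm comparison. If the first-exchange definition is kept for consistency with Protocol 9.1.3.1, add AE, SAE and fatal-AE tables from randomization for all randomized subjects by assigned arm, with never-exchanged PE subjects flagged. On either route:

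- Show post-randomization, pre-exchange events separately from screening events.
- Keep the 72-hour session-associated table for timing relative to an exchange.
- Reconcile SAP 6.4.1 with Protocol 9.7, including the as-treated grouping in both, so that a never-exchanged PE subject has one stated place.
- List the change in Section 12, with date and reason: the trial is open-label, and SAP 3.0 (15 October 2025) already postdates the last patient visit (14 April 2025).
- State that Protocol 8.3.8 labels pre-exposure AEs as unrelated, so these events will still not appear as suspected ADRs.

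The cost is SAP wording, a re-run of the AE flags and a few tables. No new data are needed. The small downside is that a few pre-exchange events will now count in the PE arm.
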